#### **5.1.4 Rationale for the exclusion criteria**

- 1)-5) To perform the efficacy evaluation of MR13A9 appropriately.
- 6)-13), 19), 21), 22) To ensure the safety of subjects.
- 14), 15) To exclude the effect of this condition on protocol adherence.
- 16) To ensure the safety of pregnant women, fetuses, and infants because the safety of MR13A9 in them has not been established.
- 17) To ensure the safety of female partners of childbearing potential and female partners who are pregnant because the safety of MR13A9 in them has not been established.
- 18) To establish a certain time interval for subjects, between administration of another study drug and administration of MR13A9 because it is impossible to rule out the possibility of an interaction between these drugs and the development of delayed adverse reactions of another investigational product as well as it is necessary to do so from an ethical aspect.
- 20) Re-registration will not be permitted because it could affect the efficacy evaluation.

### **5.2 Extension Period**

Subjects meeting all of the following criteria for entrance at the Week 6 visit during the double-blind period will enter into the extension period. Subjects not meeting the criteria for entrance will be withdrawn from the study and undergo the assessments at discontinuation promptly.

#### **5.2.1 Criteria for entrance**

- 1) Subjects not withdrawn during the double-blind period
- 2) Subjects receiving at least 14 doses of the study drug during the double-blind period
- 3) Subjects completing at least 70% of the symptom diary during the double-blind period

---

4) Subjects who are not inappropriate to enter into the extension period for safety or other reasons in the opinion of the principal investigator or subinvestigator

### **5.2.2 Rationale for the criteria for entrance**

- 1), 2) To perform the efficacy evaluation of MR13A9 appropriately.
- 3) To include subjects who can perform appropriate assessment using a symptom diary.
- 4) To ensure the safety of subjects.

## **5.3 Discontinuation of Individual Subjects**

### **5.3.1 Discontinuation criteria (discontinuation of individual subjects)**

- 1) Adverse events
  - It is necessary to withdraw the subject from the study because of the adverse event in the opinion of the principal investigator or subinvestigator.
  - The subject does not want to continue the study due to the adverse event.
- 2) Lack of efficacy (inadequate response):
  - Study continuation may cause an unacceptable risk to the subject because of the lack of efficacy of the study drug in the opinion of the principal investigator or subinvestigator.
- 3) Voluntary request for study discontinuation by the subject (Discontinuation due to an adverse event is categorized as 1) above and discontinuation due to the lack of efficacy is categorized as 2) above).
- 4) Significant protocol deviation during the study (between the date of informed consent and the end of the follow-up period)
  - Any GCP violation is found
  - After the initial study treatment, the subject is found not meeting any of the inclusion criteria or meeting any of the exclusion criteria stipulated in the protocol
  - A subject has received the study drug with drug number other than specified
- 5) Four consecutive missed doses of the study drug during the double-blind period
- 6) Seven consecutive missed doses of the study drug during the extension period
- 7) Not meeting the criteria for entrance at the Week 6 visit of the double-blind period
- 8) Pregnancy
- 9) Discontinuation of the entire study
- 10) Discontinuation of the study at the study site
- 11) Lost to observation or follow-up
  - Study continuation becomes impossible because of failure to contact the subject.
- 12) Any other cases where it is necessary to withdraw the subject from the study in the opinion of the principal investigator or subinvestigator (A detailed reason should be recorded in the case report form)

### **5.3.2 Responses to the discontinuation of any individual subject**

- If a subject meets any of the criteria described in “[5.3.1 Discontinuation criteria \(discontinuation of individual subjects\)](#)” during the study, the principal investigator or subinvestigator will immediately decide to discontinue the study. On the next dialysis day after the decision to discontinue, the prespecified assessment items at discontinuation will be measured and assessed and the date of discontinuation and the reason for discontinuation will be recorded in the case report form. The date of discontinuation will be the day when the principal investigator or subinvestigator decides to discontinue the study. If the study is discontinued during the double-blind period or the extension period, the next day of the assessments at discontinuation will be regarded as the start date of the follow-up period.
- If the study is discontinued because of the occurrence of an adverse event, the principal investigator or subinvestigator will promptly provide appropriate treatment for the subject and perform a follow-up investigation, as instructed in “[10.13.9 Follow-up investigation](#).”
- If a subject does not return to the study site, the principal investigator, subinvestigator, or clinical research coordinator will immediately investigate the reason for missed visits and the subsequent course.

## **6. Subject Consent**

### **6.1 Timing of Informed Consent**

Written informed consent must be obtained before the start of the screening period (before any protocol-specified testing, and before the start of washout for patients on nalfurafine hydrochloride).

### **6.2 Informed Consent Procedure**

The principal investigator will prepare written information and consent forms with reference to the materials and information necessary to prepare these documents provided by the sponsor (e.g., examples of written information and informed consent forms), and obtain approval of the institutional review board (IRB) in advance.

The principal investigator or subinvestigator will select subjects who have sufficiently considered the objectives of the study from the ethical and scientific standpoints. Individuals incapable of giving consent will not be selected as subjects. When selecting an individual who may have an unreasonable disadvantage because he/she does not participate in the study, the principal investigator or subinvestigator must ensure that consent is given voluntarily by the subject.

Prior to the participation of each subject in the study, the principal investigator or subinvestigator will provide the subject with a thorough explanation using the written information. The principal investigator or subinvestigator will obtain voluntary written consent for study participation (informed consent form) from the subject after giving a chance to ask questions, answering to the questions sufficiently, and confirming that the subject has understood the information sufficiently. The informed consent form will be dated and signed (or affix name and seal) by the principal investigator or subinvestigator giving the explanation and dated and signed by the subject. Any clinical research coordinator giving a supplementary explanation will also date and sign (or affix name and seal) the informed consent form.

---

The principal investigator or subinvestigator will hand the written information and a copy of the informed consent form to the subject and retain the original informed consent form at the study site.

## **7. Study Drugs**

### **7.1 Test Drug and Comparator**

#### **7.1.1 Test drug**

- 1) Code name: MR13A9
- 2) Nonproprietary name: Difelikefalin acetate (JAN)
- 3) Strength and dosage form:
  - MR13A9 17.5 µg: Pre-filled syringe containing 17.5 µg of MR13A9 per syringe
  - MR13A9 25.0 µg: Pre-filled syringe containing 25.0 µg of MR13A9 per syringe
  - MR13A9 35.0 µg: Pre-filled syringe containing 35.0 µg of MR13A9 per syringe
  - MR13A9 42.5 µg: Pre-filled syringe containing 42.5 µg of MR13A9 per syringe
- 4) Storage conditions: Store at room temperature (1°C to 30°C)

#### **7.1.2 Comparator**

- 1) Strength and dosage form:

MR13A9 placebo: Pre-filled syringe not containing MR13A9

The MR13A9 placebo is indistinguishable from MR13A9 17.5, 25.0, 35.0, or 42.5 µg.

- 2) Storage conditions: Store at room temperature (1°C to 30°C)

#### **7.1.3 Rationale for the comparator**

With reference to the “Choice of Control Group and Related Issues in Clinical Trials” (MHLW PFSB/ELD Notification No. 136 dated February 27, 2001), a placebo has been selected as a comparator to control all potential influences on the actual or apparent course of the disease other than those arising from the pharmacologic action of the test drug (natural history of the disease, subject or investigator expectations, the effect of being in a trial, use of other therapy, and subjective elements of diagnosis or assessment).

## **7.2 Packaging of the Study Drugs**

- Double-blind period

A total of 21 prefilled syringes containing MR13A9 0.5 µg/kg or placebo packaged in blister packs (18 syringes for 6-week treatment + 3 spare syringes) will be packed in 1 carton.

- Extension period

A total of 10 prefilled syringes containing MR13A9 0.5 µg/kg packaged in blister packs (9 syringes for 3-week treatment + 1 spare syringe) will be packed in 1 carton.

## 7.3 Labeling

Details of labeling will be provided in a separate written procedure.

## 7.4 Management of the Study Drugs

The study drug manager will manage and store the study drugs appropriately, as stipulated separately in the written procedure.

# 8. Study Methods

## 8.1 Study Design

- Double-blind period

A placebo-controlled, multicenter, randomized, double-blind, parallel-group study

- Extension period

A multicenter, open-label study

	Screening period 2 weeks	Double-blind period 6 weeks	Extension period 52 weeks	Follow-up period 1 week
Placebo group				
		Placebo	MR13A9 0.5 µg/kg	
		Conditionally permitted concomitant medications (anti-itch drugs)		
MR13A9 0.5 µg/kg group		MR13A9 0.5 µg/kg	MR13A9 0.5 µg/kg	
		Conditionally permitted concomitant medications (anti-itch drugs)		

Figure 8.1-1 Study Design

## 8.2 Dosage and Administration

### 8.2.1 Screening period

A 2-week period before entry into the double-blind period is defined as the screening period, during which subjects will receive no study drug. Subjects will continuously use any conditionally permitted concomitant medications (e.g., anti-itch drugs) used at the start of the screening period.

### 8.2.2 Double-blind period

In addition to the use of conditionally permitted concomitant medications (e.g., anti-itch drugs) used at the start of the screening period, the study drug will be injected into the venous line of the dialysis circuit at the end of each dialysis session for 6 weeks (3 times weekly, 18 times in total). The dose of the study drug will be determined based on the subject's dry weight before dialysis on the start day of the screening period according to [Table 8.2.2-1](#).

If any dialysis circuit trouble precludes injection through the dialysis circuit, the study drug will be administered directly intravenously. If an extra fourth dialysis session is required within the week, the study drug will be administered (up to 4 times weekly). If only the extracorporeal ultrafiltration method is used, the study drug will not be administered.

**Table 8.2.2-1 Doses**

Dry weight	Injected volume	MR13A9 dose	
		0.5 µg/kg group	Placebo group
< 45.0 kg	0.35 mL	17.5 µg	0 µg
≥ 45.0 kg, < 65.0 kg	0.35 mL	25.0 µg	0 µg
≥ 65.0 kg, < 85.0 kg	0.35 mL	35.0 µg	0 µg
≥ 85.0 kg	0.35 mL	42.5 µg	0 µg

### 8.2.3 Extension period

In addition to the use of conditionally permitted concomitant medications (e.g., anti-itch drugs) used at the start of the screening period, the study drug will be injected into the venous line of the dialysis circuit at the end of each dialysis session for 52 weeks (3 times weekly, 156 times in total). Study treatment in the extension period will be started at Week 6. The dose of the study drug will be determined according to [Table 8.2.2-1](#), and the dose of the study drug from Week 6 to immediately before Week 34 will be determined based on the subject's dry weight before dialysis at Week 6. The dose of the study drug after Week 34 will be determined based on the subject's dry weight before dialysis at Week 34. The study drug will not be administered at Week 58.

If any dialysis circuit trouble precludes injection through the dialysis circuit, the study drug will be administered directly intravenously. If an extra fourth dialysis session is required within the week, the study drug will be administered (up to 4 times weekly). If only the extracorporeal ultrafiltration method is used, the study drug will not be administered.

### 8.2.4 Follow-up period

A 1-week period after the assessments at discontinuation or a 1-week period after the end of the extension period is defined as the follow-up period, during which subjects will receive no study drug.

### 8.2.5 Rationale for the doses and the duration of treatment

In a Japanese phase II clinical study (Study MR13A9-4), intravenous administration of MR13A9 0.25, 0.5, and 1.0 µg/kg or placebo 3 times weekly for 8 weeks resulted in significant improvement of pruritus in 0.5 and 1.0 µg/kg groups compared with the placebo group. In addition, there was a dose-response relationship showing a constant effect of MR13A9 at doses of 0.5 µg/kg and higher. As for safety, MR13A9 at up to 1.0 µg/kg was tolerated, but adverse events occurred frequently in the 1.0 µg/kg group. The phase II study in the United State (Study CLIN2101) and phase III study (Study CLIN3102) also confirmed the superiority of the MR13A9 0.5 µg/kg group to the placebo group. Based on the above, it was considered appropriate to select 0.5 µg/kg of MR13A9 as the recommended clinical dose.

In Study MR13A9-4, the effect of MR13A9 to improve itching was constant after Week 4, and all adverse drug reactions occurred before Week 6. Accordingly, 4-week and 6-week periods in the double-blind period were established to allow the efficacy and safety evaluations of MR13A9, respectively. In addition, a 52-week extension period was established to assess the safety of long-term treatment with MR13A9 with reference to the "Extent of Population Exposure to Assess Clinical Safety for Drugs Intended for Long-Term Treatment of Non-Life-Threatening Conditions" (ELD Notification No. 592 dated May 24, 1995).

## 8.3 Concomitant Treatments

Subjects may use any drug used to treat symptoms of chronic renal failure or drug used to treat complications at the start of the screening period without changing its dosage and administration whenever possible until the end of the follow-up period. The dosage and administration of any concomitant medication may be changed for safety reasons including adverse events. Any centrally acting concomitant drug should be used with attention to possible central adverse events.

A summary of concomitant treatments is shown in [Table 8.3-1](#).

**Table 8.3-1 Concomitant Treatments**

	Screening period	Double-blind period	Extension period	Follow-up period
Concomitant medications	Permitted (The dosage and administration should not be changed whenever possible.)			
Prohibited concomitant medications	Not permitted			
Conditionally permitted concomitant medications	Permitted (The dosage and administration should not be changed or newly used.)		Permitted (The dosage and administration should not be changed or newly used whenever possible.)	
Prohibited concomitant therapies	Not permitted			

### 8.3.1 Prohibited concomitant medications

Between the start of the screening period and the end of the follow-up period, use of the drugs listed in [Table 8.3.1-1](#) will be prohibited.

**Table 8.3.1-1 Prohibited concomitant medications**

Class	Common drugs
1) Opioids	Nalfurafine hydrochloride, morphine, fentanyl, oxycodone, buprenorphine, pentazocine, codeine phosphate, dihydrocodeine, etc.
2) Opioid antagonists	Naloxone hydrochloride, eptazocine hydrobromide, naldemedine tosylate, etc.
3) Investigational products other than MR13A9	Various kinds

### 8.3.2 Conditionally permitted concomitant medications

Between the start of the screening period and the end of the double-blind period (or the time of withdrawal during the double-blind period), subjects may use the drugs listed below that have been used since before the screening period without changing their dosage and administration. In addition, the drugs listed below should not be newly used. The dosage and administration at the start of the screening period should not be changed or newly used.

Between the start of the extension period and the end of the follow-up period, the dosage administration should not be changed or newly used whenever possible.

- 1) Drugs indicated for the treatment of itching (prescription/nonprescription)
- 2) Drugs to treat itching (prescription/nonprescription)
- 3) Moisturizing drugs (prescription/nonprescription)
- 4) Steroids (excluding inhalants, nasal drops, ear drops, eye drops, and eye ointments)

---

- 5) Capsaicin (topical)
- 6) In-hospital drugs formulated with any of the drugs listed 1) to 5) above
- 7) Pregabalin, gabapentin
- 8) Antidepressants, anxiolytics

Among the drugs listed in 1) to 6) above, however, topical use of any prescription/nonprescription drug used to treat itching caused by chronic renal failure or any complication of chronic renal failure will not be restricted (concomitant medications for local itching caused by insect stings, chilblains, contact dermatitis, etc. will not be restricted).

Use of any combination product that contains ingredients indicated for itching but is not indicated itself for itching will not be restricted.

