### 5.1.3 Exclusion criteria

- 1) Patients with itching caused by conditions other than chronic renal failure or complications of chronic renal failure, which could affect the efficacy evaluation in the opinion of the principal investigator or subinvestigator (e.g., atopic dermatitis, chronic urticaria)
- 2) Patients with concurrent hepatic cirrhosis
- 3) Patients who used nalfurafine hydrochloride within 2 weeks prior to the start of the screening period
- 4) Patients who received phototherapy to treat itching within 4 weeks prior to the start of the screening period
- 5) Patients who previously received any study drug (including placebo) in a clinical study of MR13A9
- 6) Patients with any adverse drug reaction to nalfurafine hydrochloride in the past who are ineligible for study participation in the opinion of the principal investigator or subinvestigator
- 7) Patients with drug hypersensitivity to opioids
- 8) Patients whose laboratory data at the start of the screening period meet any of the criteria (1) to (3) below:
  - (1) ALT: > 2.5 times the upper limit of normal
  - (2) AST: > 2.5 times the upper limit of normal
  - (3) Total bilirubin: > 2 times the upper limit of normal
- 9) Patients with congestive heart failure (NYHA functional class IV) ([Appendix 3](#))
- 10) Patients with concurrent malignancy or a history of malignancy within 5 years prior to the informed consent procedure
- 11) Patients with concurrent or previous drug abuse (defined as illicit drug use)
- 12) Patients with concurrent or previous alcoholism
- 13) Patients with a history of severe drug hypersensitivity (anaphylactic shock, etc.)
- 14) Patients with concurrent depression, schizophrenia, or dementia
- 15) Patients with a concurrent mental disorder that could affect the evaluation of the investigational product
- 16) Female patients who are pregnant, breastfeeding, intending to become pregnant between the informed consent procedure and the end of the follow-up period, or unwilling to use appropriate methods to prevent conception

---

- 17) Male patients who are unwilling to use appropriate methods to prevent conception between the start of study treatment and 12 weeks after the day of the final dose

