#### **8.3.4 Rationale for the prohibited concomitant medications, conditionally permitted concomitant medications, and prohibited concomitant therapies**

To exclude their effects on the efficacy evaluation of MR13A9.

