## 9. Subject Instructions and Management

The principal investigator or subinvestigator should sufficiently explain the significance and objectives of the study to subjects, and instruct and manage them especially for the following:

- 1) Confirm the absence of somnolence, dizziness, or similar symptoms after receiving the study drug and return home. Report any symptoms to the principal investigator or subinvestigator.

---

- 2) Pay attention during hazardous machine operation and automobile driving during the treatment period.
- 3) Maintain the symptom diary in subject every day. Report any device deficiencies to the principal investigator or subinvestigator.
- 4) Take all prescribed drugs other than the study drug properly as instructed.
- 5) Be sure to visit the study site as scheduled. Inform the study site in advance if it is impossible to visit for some unavoidable reason.
- 6) Visit the study site at the same time at every visit whenever possible during the study period.
- 7) Report the drug(s) used currently to the principal investigator or subinvestigator before participation in the study. Consult the principal investigator or subinvestigator about any new drug prescribed at other medical departments or hospitals or any over-the-counter drug before use. Report to the principal investigator or subinvestigator immediately if it was inevitable to use any drug without consultation.
- 8) Be sure to report in advance any visit to another department or hospital during the study period to the principal investigator or subinvestigator and report your participation in the study to the doctor at the department or hospital. If it is impossible to report in advance for unavoidable reasons such as an emergency visit, report your participation in the study to the doctor at the department or hospital and immediately report the visit to the department or hospital as well as prescribed drugs and other information to the principal investigator or subinvestigator.
- 9) Immediately inform the principal investigator or subinvestigator about any abnormalities in your body after undergoing tests at the end of the follow-up period or at the end of the follow-up investigation.
- 10) Women of childbearing potential must avoid intercourse or use appropriate contraceptive methods when having intercourse during the study period. Immediately inform the principal investigator or subinvestigator about any suspected pregnancy during the study period.

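### Protocol 8.3.2 and the Synopsis misstate the topical exemption: as worded it frees treatment of renal-failure itch, while its own bracket describes only non-renal local itch

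*Protocol*

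**What the plan says.** Protocol 8.3.2 lists eight groups of conditionally permitted drugs. From the start of screening to the end of the double-blind period they may be continued, but not changed or newly started. Items 1) to 6) cover drugs indicated for or used against itching, moisturizers, steroids, topical capsaicin and in-hospital preparations of these.

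An exception follows for items 1) to 6). Topical use of any prescription or nonprescription "drug used to treat itching caused by chronic renal failure or any complication of chronic renal failure will not be restricted". A bracket is attached: "concomitant medications for local itching caused by insect stings, chilblains, contact dermatitis, etc. will not be restricted". The Synopsis carries the same sentence and bracket.

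Protocol 8.3.4 gives the purpose of these restrictions: "To exclude their effects on the efficacy evaluation of MR13A9".

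The PPS definition (Protocol 14.1, repeated in SAP section 2) removes subjects who change or newly use a conditionally permitted medication before Week 4. It does not mention the topical exemption. The FAS, the primary efficacy set, has no condition on concomitant drugs.

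**The concern.** Itch caused by chronic renal failure is the indication, and inclusion criterion 5 requires every subject to be on at least one anti-itch or moisturizing drug already. A rule that frees topical treatment of that itch allows background therapy for the target symptom to be stepped up during the blinded comparison. This is what 8.3.4 says the restrictions are meant to prevent.

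Two things are at stake. First, if subjects with persistent itch add or intensify topical treatment, and do so more often on placebo, the Week 4 difference narrows. Second, the same act could be handled differently by different people: one applies the exemption sentence and records no deviation, another applies the general no-change rule and excludes the subject from the PPS. The PPS is the set used to check the robustness of the primary result.

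Only topical use is affected. Systemic anti-itch drugs and steroids, pregabalin, gabapentin, antidepressants and anxiolytics stay restricted on any reading.

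**Working it through.** **Step 1: the sentence against its bracket.** The main clause exempts itch whose cause is renal failure or a complication of it. The bracket's examples all have another cause. For a topical drug newly started in Week 3:

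| Reason for the topical start | Main clause, literally | Bracket | Probable intent |
|---|---|---|---|
| Renal-failure itch | free | not covered | restricted |
| Insect sting or contact dermatitis | not covered | free | free |

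The main clause and the bracket agree in neither row. This is the direct contradiction, and it needs no other text.

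**Step 2: which half is wrong.** Two other places point the same way, as support for intent rather than as further contradictions.
- The purpose in 8.3.4 is defeated by the literal clause and served by the bracket.
- Exclusion criterion 1 (Protocol 5.1.3) uses nearly the same phrase with a qualifier that the exemption lacks: "Patients with itching caused by conditions other than chronic renal failure or complications of chronic renal failure". This suggests which words may have dropped out.

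Table 8.3-1 shows the double-blind restriction with no topical exemption. That is weak support, because 8.3 introduces the table as a summary.

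**Step 3: does another text correct it?** No. The Synopsis repeats the sentence. Protocol section 9, item 7 tells subjects: "Consult the principal investigator or subinvestigator about any new drug prescribed at other medical departments or hospitals or any over-the-counter drug before use". That sends the question to the investigator, whose reference is 8.3.2. The SAP repeats the PPS rule without clarifying the exemption.

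**Step 4: size.** The plan's own figure reproduces. Inputs from Protocol 8.6.2.1: difference 1.0, SD 2.0, two-sided 5%, power 90%.
- Normal approximation: n = 2 × (1.960 + 1.282)² × 2.0² / 1.0² = 84.1, so 85 per group.
- Exact two-sample t-test: 85.03, so 86 per group as stated. Power at 86 per group is 90.3%.

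Dilution under the literal reading would be

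loss = (share stepping up topicals on placebo − share on active) × mean NRS gain from stepping up.

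The documents give neither the shares nor the gain, so the loss cannot be computed. As illustration only, with 86 per group and SD 2.0, a true difference cut to 0.9 gives 83.5% power and one cut to 0.8 gives 74.2%. Nothing in the documents says that either cut is realistic. The primary analysis is a mixed model for repeated measures, so these are planning values.

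**The case against.** The best defence is that little beyond the bracket truly conflicts with the main clause, and most of this stands.
- A clause opening with 'however' may free items on its own list, so the listing of topical capsaicin is not a contradiction.
- Table 8.3-1, as a summary, also omits the exemption for combination products, which nobody disputes. Its silence on topicals proves little.
- The general rule in 8.3 asks for drugs to be continued "without changing its dosage and administration whenever possible until the end of the follow-up period", which is a soft request.
- 8.3.4 and exclusion criterion 1 bear on intent only.

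A reader might infer that the protocol contradicts itself in many places, or that Table 8.3-1 positively bars what the sentence allows. The documents do not support that. There is one contradiction, inside one sentence that is printed twice.

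It can also be argued that the bracket repeats its own verb and so might be a second, additional exemption. The grammar allows this. But topical treatment of both renal itch and local non-renal itch would then be free, which leaves little of the topical restriction and still defeats 8.3.4. It is the less natural reading, though only the sponsor can exclude it.

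Finally, the practical exposure is limited. The PPS analysis is supplementary. Protocol 10.4.1 records route, duration and indication for nearly all drugs, so topical starts for renal itch can be identified. Protocol 14 leaves subject and data handling to a decision before lock. These points limit the damage and lower the severity, but they do not correct the instruction given to sites.

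**Conclusion.** The exemption is wrong as written, with minor to moderate severity. It is an operative rule that, followed literally, permits what the section exists to prevent, and no other text states it correctly. That the main clause and bracket conflict is certain. That the intent was non-renal itch is a well-supported inference. Whether words were lost in translation is not known.

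The effect on the treatment difference is not derivable and is zero if sites applied the probable meaning. If the literal text was followed, the expected direction is dilution, on the assumption that step-up would be more frequent on placebo. PPS membership would be unclear for the subjects concerned.

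A reader might infer more, and the documents do not support it:
- **False superiority.** With the blind intact and no drug effect, both arms would have the same freedom and the same reason to use topicals, so no spurious advantage arises.
- **A compromised primary analysis set.** FAS membership does not depend on concomitant drugs.
- **A demonstrated power loss.** The figures at 0.9 and 0.8 illustrate sensitivity and are not evidence of harm.
- **Actual misuse.** Nothing shows that any site acted on the literal text.

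**What to change.** Confirm the intended rule against the source-language text. Then replace the sentence in Protocol 8.3.2 and the Synopsis with wording such as:

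> For items 1) to 6), topical treatment, prescribed or over the counter, of local itching that is caused neither by chronic renal failure nor by any of its complications (for example insect stings, chilblains or contact dermatitis) is exempt from this restriction.

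The 'neither … nor' form matters. Simply inserting the qualifier from exclusion criterion 1 could still be read as exempting itch from complications of renal failure. Placing 'local' in the main clause keeps the exemption from covering extensive topical treatment.

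In Protocol 14.1 and SAP section 2, add one clause to the PPS rule: a topical start or change for renal-failure itch before Week 4 counts as an exclusion, and exempt local use does not.

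The cost is one sentence in two places and one clause in each document. Under Protocol 15.2 the protocol change needs agreement between sponsor and principal investigator, and IRB approval unless it is purely administrative. If the fault lies only in the translation, correcting the translation may suffice. No new data are needed, because Protocol 10.4.1 already records the date, detail and reason for each change.
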